2.3 Benefit/Risk Assessment

At the time of study initiation the identified and potential risks with bintrafusp alfa monotherapy were manageable and no new safety signals emerged in the Phase I studies (EMR200647-001, MS200647-0008) compared with therapies targeting PD-L1 or TGF- β . The following have been identified as important identified risks for bintrafusp alfa: immune-related adverse events (irAEs; immune-related pneumonitis, immune-related hepatitis, immune-related colitis, immune-related nephritis and renal dysfunction, immune-related endocrinopathies [thyroid disorders, adrenal insufficiency, Type 1 diabetes mellitus, pituitary disorders], immune-related rash and other irAEs [myositis, myocarditis, encephalitis]), TGF- β inhibition mediated skin reactions, anemia, and bleeding adverse events. The overall incidence and severity for irAEs is found to be consistent across bintrafusp alfa studies and similar to the known safety profile of approved anti-PD-L1 agents (Brahmer 2018). Infusion-related reactions (IRRs) are classified as identified risk for the treatment with bintrafusp alfa. Infusion-related reactions observed with bintrafusp alfa were similar to those seen with monoclonal antibodies. At the time of study initiation, the overall bintrafusp alfa related IRRs were observed to be < 5%; they were typically low-grade (Grade 1/2) severity and did not require permanent treatment discontinuation.

Dermatologic AEs related to TGF- β inhibition (including keratoacanthomas [KA] and cutaneous squamous cell cancers) are an important identified risk with bintrafusp alfa not seen with other programmed death-1 (PD-1)/PD-L1 antibodies. These lesions were previously observed in participants with genetic mutations in the TGF- β receptor (i.e., Ferguson-Smith syndrome), and participants treated with the TGF- β targeting agent fresolimumab (Goudie 2011, Morris 2014). At the time of study initiation in the Phase I studies, these treatment-emergent TGF- β inhibition mediated skin reactions were observed in approximately 11% of participants, were well managed with simple excision (or spontaneous resolution) and did not require any participant to discontinue treatment (refer to IB). The risk of these lesions with bintrafusp alfa was considered manageable, especially in the context of encouraging clinical activity in several tumor types.

No additional/new safety signals emerged in the TNBC cohort of Study EMR200647-001 compared with other tumor types (Spira 2019).

In consideration of the following items, the benefit/risk assessment is considered favorable to conduct this study of bintrafusp alfa in participants with high expressing HMGA2 TNBC:

- The high unmet medical need and absence of an efficacious standard of care for patients with TNBC who have progressed after their first line of chemotherapy.
- The bifunctional mode of action of bintrafusp alfa, targeting 2 complementary and nonredundant signaling pathways within the tumor immune microenvironment.
- The consideration that bintrafusp alfa targets TGF- β (demonstrated in preclinical studies as well as pharmacodynamically in Phase I dose-escalation participants), and that HMGA2 is downstream of the TGF- β signaling pathway (see Section 2.1 and Section 2.2).
- The signal for considerable clinical activity of bintrafusp alfa in participants in Study EMR200647-001 with TNBC expressing high levels of HMGA2 (50% ORR, 62.5% disease control rate) (Locke 2019b).
- The manageable safety profile of bintrafusp alfa observed in the Phase I studies, including TNBC participants.

More detailed information about the known and expected benefits and risks and reasonably expected AEs of bintrafusp alfa may be found in Section 4.2 and the current IB.

Based on the available nonclinical and clinical data to date, the conduct of the study, as specified in this protocol, is considered justifiable.

3 Objectives and Endpoints

Table 3 Study Objectives and Endpoints

Objectives	Endpoints (Outcome Measures)
Primary	
• To evaluate clinical efficacy of bintrafusp alfa in participants with TNBC with high HMGA2 expression, based on ORR	• Confirmed objective response according to RECIST 1.1 assessed by an IRC
Secondary	
• To evaluate clinical efficacy of bintrafusp alfa based on DOR	• DOR according to RECIST 1.1 assessed by an IRC
• To evaluate clinical efficacy of bintrafusp alfa based on DRR	• Durable response of at least 6 months assessed by an IRC
• To evaluate clinical efficacy based on PFS	• PFS according to RECIST 1.1 assessed by an IRC
• To evaluate ORR, DOR, DRR, and PFS by Investigator read	• Objective response, DOR, DRR, and PFS according to RECIST 1.1 as assessed by the Investigator
• To evaluate clinical efficacy based on OS	• OS
• To evaluate clinical safety of bintrafusp alfa	• Occurrence of TEAEs and treatment-related AEs including AEs of special interest

Objectives	Endpoints (Outcome Measures)

 To characterize the PK profile of bintrafusp alfa 	
 The concentration observed immediately at the end of infusion (C_{EOI}) of bintrafusp alfa The concentration observed immediately before next dosing (corresponding to predose or trough concentration [C_{trough}] for multiple dosing) of bintrafusp alfa

 To characterize the immunogenicity of bintrafusp alfa 	
 Immunogenicity of bintrafusp alfa as measured by ADA assay from Screening through Safety Follow-up Visit up to 28 days after last treatment
CCI 	   

ADA=antidrug antibody, AE=adverse event, DOR=duration of response, DRR=durable response rate, HMGA2=High Mobility Group AT-Hook 2, ir=immune-related, IRC=Independent Review Committee, ORR=Objective response rate, OS=overall survival, PD-L1=programmed death-ligand 1, PFS=progression-free survival, PK=pharmacokinetic, RECIST 1.1=Response Evaluation Criteria in Solid Tumors Version 1.1, TEAE=treatment-emergent adverse event, TMB=tumor mutational burden, TNBC=triple negative breast cancer.

4 Study Design

4.1 Overall Design

This is a Phase II, multicenter, single-arm, open label study to evaluate bintrafusp alfa monotherapy in participants with TNBC who express high levels of HMGA2 as determined by a centralized reverse transcriptase-polymerase chain reaction (RT-PCR) test with predefined cutoff. Participants must have progressed during or after first-line of chemotherapy.

The primary objective is to evaluate the clinical efficacy of bintrafusp alfa based on the ORR as assessed by an IRC. The key secondary objectives are duration of response (DOR), durable response rate (DRR), progression-free survival (PFS), OS, and safety. Tumor response evaluations based on Response Evaluation Criteria in Solid Tumors Version 1.1 (RECIST 1.1) ([Eisenhauer 2009](#)) will be performed every 8 weeks until 12 months after the first administration of bintrafusp alfa and then every 12 weeks until confirmed disease progression, unacceptable toxicity, or occurrence of any criterion for withdrawal from the study.

The study plans to enroll approximately 29 eligible participants globally with competitive enrollment.

The study includes:

- Prescreening (a Prescreening informed consent form [ICF] will be used for HMGA2 biomarker analysis and collection of baseline clinical history). Positive HMGA2 test results on tumor tissue is required to enter formal study Screening (see [Table 1](#)).
- Up to 28-day Screening period.
- Treatment with bintrafusp alfa at a dose of 1200 mg intravenously once every 2 weeks until confirmed PD, unacceptable toxicity, study withdrawal, or death.
- In the case of PD, treatment may continue past the initial determination of PD or confirmed PD, if the participant's performance status (PS) has remained at least stable, and if in the opinion of the Investigator, the participant will benefit from continued treatment and if other criteria are fulfilled as outlined in the protocol (see [Section 7.1.3](#)).
- In the case of SD, PR, or complete response (CR), treatment should be continued until the end of 24 months. If the Investigator believes that a participant will benefit from treatment beyond 24 months, it may be permissible after discussion with the Medical Monitor and the Sponsor Medical Responsible.
- Safety Follow-up will continue until 12 weeks after the last dose of bintrafusp alfa. The 12-week Safety Follow-up is allowed to be conducted via telephone calls or patient chart reviews, unless there is medical necessity requiring a clinical visit.
- Long-term Follow-up for progression and survival should be performed every 12 weeks after the Safety Follow-up according to the Schedule of Activities ([Table 1](#)). Long-term Follow-up should be performed by patient chart reviews or telephone calls unless a clinical visit is indicated.

The overall study design is shown in [Figure 1](#). A detailed Schedule of Activities is provided in [Section 1.3](#).

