	Day -28 to Treatment Assignment	V1	V2	V3	V4	V5	V6	V7	V8	V9	Until PD	On the Day of or Within 7 Days of Decision to Discontinue	28 Days (± 5 Days) After Last Treatment	12 Weeks (± 2 Weeks) After Last Treatment	Every 12 Weeks (± 2 Weeks)		
		W1	W3	W5	W7	W9	W11	W13	W15	W17							
	D1	D15	D29	D43	D57	D71	D85	D99	D113								
β-hCG pregnancy test		X	X		X		X		X		X	Q4W		X	X ⁱ		β-hCG should be determined from serum at Screening and from a urine or serum sample thereafter. Results of the most recent pregnancy test should be available prior to dosing of study intervention. If a confirmation of a participant's postmenopausal status is necessary, FSH and estradiol tests will be performed at Screening. i: Participants may go to local laboratory to perform pregnancy test. Clinical visit is not required.
T4 and TSH		X			X		X			Q6W			X				

Assessments & Procedures	Pre screening	Screening	Intervention Period (\pm 3 days)										End-of-Treatment Visit	Safety Follow-up Visit		Long-term Follow-up	Notes
	Day -28 to Treatment Assignment	V1	V2	V3	V4	V5	V6	V7	V8	V9	Until PD	On the Day of or Within 7 Days of Decision to Discontinue	28 Days (\pm 5 Days) After Last Treatment	12 Weeks (\pm 2 Weeks) After Last Treatment	Every 12 Weeks (\pm 2 Weeks)		
			W1	W3	W5	W7	W9	W11	W13	W15							
		D1	D15	D29	D43	D57	D71	D85	D99	D113							
+Tumor Assessments																	
Tumor evaluation /staging (CT scan/MRI/other established methods)		X					X					X	Q8W up to 12 months, then Q12W		X ^j	See Section 8.1. j: For participants discontinuing treatment due to reason other than PD, perform tumor evaluation Q8W until 12 months (e.g.W49), then Q12W until confirmed PD or study discontinuation. The window for tumor evaluation is \pm 7 days. The Intervention Period window of (\pm 3 days) is not applicable for tumor evaluations.	
Subsequent anticancer therapy (any line)														X	X	X	
Survival follow-up															X		

Assessments & Procedures	Pre screening	Screening	Intervention Period (± 3 days)										End-of-Treatment Visit	Safety Follow-up Visit		Long-term Follow-up	Notes			
	Day -28 to Treatment Assignment	V1	V2	V3	V4	V5	V6	V7	V8	V9	Until PD	On the Day of or Within 7 Days of Decision to Discontinue	28 Days (± 5 Days) After Last Treatment	12 Weeks (± 2 Weeks) After Last Treatment	Every 12 Weeks (± 2 Weeks)					
		W1	W3	W5	W7	W9	W11	W13	W15	W17			D1	D15	D29	D43	D57	D71	D85	D99
PK, ADA and Biomarker																				

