- Drug must not be given to a known pregnant participant (see Appendix 3).
- Use of a prohibited concomitant drug, as defined in Section 6.5.2, where the predefined consequence is withdrawal from the study intervention.

In case of discontinuation from the study intervention:

- The day of End-of-Treatment Visit will correspond to the day of withdrawal (or within 7 days).
- An attempt should be made to perform all assessments scheduled for the End-of-Treatment Visit if possible. If not possible, the most clinically relevant assessments and appropriate eCRFs for the End-of-Treatment Visit should be prioritized as feasible.
- Participants will be asked to continue Safety Follow-up and Survival Follow-up, which includes the collection of data on survival, and subsequent anticancer therapy. After completion of the follow-up period or after the End-of-Treatment Visit, whichever is applicable, the appropriate eCRF section for Study Termination must be completed.
- If the participant is enrolled into a new study or any new therapy post-withdrawal from study intervention, the Safety Follow-up Visit should be scheduled prior to the start of the new treatment irrespective of the 28-day Safety Follow-up period.

The Schedule of Activities specifies the data to collect at study intervention discontinuation and follow-up, and any additional evaluations that need to be completed.

7.1.1 **Temporary Discontinuation**

See Section 6.8 and Section 6.9 for guidance on temporary discontinuation from study intervention.

7.1.2 **Rechallenge**

7.1.2.1 **Reinitiation**

One reinitiating course of treatment at the same dose and schedule and treatment duration up to 24 months is allowed at the discretion of the Investigator and agreement of the Medical Responsible for:

- Participants who are experiencing SD, PR, or CR at the time of discontinuation, and then subsequently develop disease progression after stopping therapy, but prior to the End of the Study.

OR

- Participants who are discontinued due to an AE that are subsequently well managed or resolved after stopping therapy, but prior to the End of the Study.

The participant should reinitiate treatment at the treatment phase visit where they left off according to the Schedule of Activities (Table 1). Participants who reinitiate treatment should stay on study and should be treated and monitored according the Schedule of Activities for the rest of the study.

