8.1 Efficacy Assessments and Procedures

Contrast-enhanced computed tomography (CT) imaging of chest/abdomen/pelvis covering the area from the superior extent of the thoracic inlet to well below the symphysis pubis is the first choice of imaging modality. If a participant should not receive iodinated contrast medium, or due to radiation protection reasons, magnetic resonance imaging (MRI) of the same area, using gadolinium enhancement according to local procedure as permitted in conjunction with unenhanced CT of the chest from the thoracic inlet to the inferior costophrenic recess should be done. Regarding MRI for new lesions, in case of doubt, possible new lesions should be followed up on serial MRI before new disease is definitively confirmed. Alternatively, biopsy can be done. The same method should be used per participant throughout the study and preferably the same machines. Brain enhanced MRI (preferably) or enhanced brain CT and/or bone scans should be performed at baseline only for participants suspected to have metastases in these sites. A central

imaging laboratory will be used to read and interpret all CT/MRI/bone scan data; however, treatment decisions will be made by the treating Investigator.

Baseline scans are taken within 28 days prior to treatment. Disease must be measurable with at least 1 uni-dimensionally measurable lesion outside the CNS by RECIST 1.1 assessed by the Investigator. All the scans performed at baseline that are required for RECIST 1.1 assessment need to be repeated at subsequent visits for tumor assessment using the same method, except for brain or bone scans that are negative at baseline. For brain or bone scans that are negative at baseline, no follow-up scans are performed unless there are new symptoms or biochemical changes which suggest PD in these regions. In general, lesions detected at baseline need to be followed using the same imaging methodology and preferably the same imaging equipment at subsequent tumor evaluation visits.

Assessments previously obtained as part of routine clinical care may be used as the baseline assessment if performed within 28 days prior to start of treatment and satisfies tumor assessment requirements as noted in this section.

Participants will be evaluated every 8 weeks within the first 12 months of the participant's first dose, then every 12 weeks through Long-term Follow-up, as scheduled in [Table 1](#).

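### Protocol 4.1 lists unacceptable toxicity as an end to tumor evaluations, contradicting Table 1 note j, which continues scans after any treatment stop not due to PD

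*Protocol*

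**What the plan says.** Protocol 4.1 sets tumor response evaluations every 8 weeks for 12 months from first dose, "then every 12 weeks until confirmed disease progression, unacceptable toxicity, or occurrence of any criterion for withdrawal from the study".

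Note j to the Schedule of Activities (Protocol Table 1) says: "For participants discontinuing treatment due to reason other than PD, perform tumor evaluation Q8W until 12 months (e.g.W49), then Q12W until confirmed PD". It names study discontinuation as the only other end. Toxicity is a reason other than PD, so note j covers it.

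Protocol 8.1 continues evaluations "then every 12 weeks through Long-term Follow-up, as scheduled in" Table 1.

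Protocol 7.1, on what happens after study intervention is discontinued, says: "Participants will be asked to continue Safety Follow-up and Survival Follow-up, which includes the collection of data on survival, and subsequent anticancer therapy". It does not name imaging. It then adds: "The Schedule of Activities specifies the data to collect at study intervention discontinuation and follow-up, and any additional evaluations that need to be completed".

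On Long-term Follow-up, Protocol 4.1 says: "Long-term Follow-up for progression and survival should be performed every 12 weeks after the Safety Follow-up according to the Schedule of Activities". The default mode is remote: "Long-term Follow-up should be performed by patient chart reviews or telephone calls unless a clinical visit is indicated". The Synopsis (1.1) carries the same two statements.

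**The concern.** Unacceptable toxicity is a reason to stop drug. It is not a reason to stop measuring disease in someone who has not progressed. Section 4.1 makes it both, and the explicit rule for scans after a stop without PD sits in a table footnote. A site that works from 4.1, reads the follow-up bullet in 7.1 and sees telephone or chart review as the default could reasonably stop scanning. A site that works from note j would continue.

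DOR, durable response (DRR) and PFS are read by the IRC from images, and a telephone call supplies none. If scanning ends because of toxicity, follow-up is cut short for a reason that may be related to outcome. Such stops are foreseen: Protocol 6.8, 6.9.5.1 and Appendix 5 contain permanent-discontinuation rules for several kinds of treatment-related event. The primary endpoint is also exposed, because a response needs a second scan to be confirmed.

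**Working it through.** **1. The plan's own figure.** Inputs from the Synopsis: n = 29, true ORR 30%, benchmark 10%, exact 95% CI. The Clopper-Pearson lower limit is 8.0% at 6/29 and 10.3% at 7/29, so the criterion is at least 7 responders.
- P(X ≥ 7 | 29, 0.30) = 0.812, which reproduces the stated 81%.
- P(X ≥ 7 | 29, 0.10) = 0.0216, inside the 2.5% one-sided level in SAP 9.

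Neither figure depends on how long responders are scanned, so the fix leaves both as they are.

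**2. Which text is the outlier.** Take a participant who stops for toxicity without PD. Protocol 4.1 ends her scans; note j and 8.1 continue them. Two further texts side with note j:
- Protocol 7.1.2.1 allows reinitiation after an AE-related stop, but expects regular documented scans up to the restart. A site following 4.1 would leave her short of that condition.
- SAP 14.4 ends the scan schedule at progression and does not mention toxicity.

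**3. Effect on DOR.** Protocol Table 11 censors PFS at the last adequate tumor assessment when there is no event, and applies the same rules to DOR. SAP 14.6 gives DOR = (last date − first response date + 1)/30.4375. Nominal scan days are 57, 113 and every 56 days after that.

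| Last scan | First response Day 57 | First response Day 113 |
|---|---|---|
| Day 113 | 57/30.4375 = 1.87 months | – |
| Day 169 | 113/30.4375 = 3.71 | 57/30.4375 = 1.87 |
| Day 225 | 169/30.4375 = 5.55 | 113/30.4375 = 3.71 |
| Day 281 | 225/30.4375 = 7.39 | 169/30.4375 = 5.55 |
| Day 337 | – | 225/30.4375 = 7.39 |

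On nominal days a Day 57 responder needs the Day 281 scan to pass 6 months, and a Day 113 responder needs Day 337. The ±7-day scan window barely shifts this: only at its extremes, Day 50 to Day 232, does the earlier scan suffice (183/30.4375 = 6.01 months).

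**4. Effect on DRR.** Under Protocol Table 11 a DOR censored before 6 months is a failure, and one censored at 6 months or later is a success. Suppose a PR at Day 57 is confirmed at Day 113, drug stops for toxicity at Day 120, and disease stays controlled to Day 281. Literal 4.1 gives 1.87 months and a failure; note j gives 7.39 months and a success. Each such responder moves DRR by 1/29 = 3.4 points. For illustration, with assumed counts, 6/29 = 20.7% (exact 95% CI 8.0% to 39.7%) becomes 5/29 = 17.2% (5.8% to 35.8%). At a 30% ORR about 0.30 × 29 = 8.7 responders are expected. If 1 to 3 of them were affected (an assumption), the shift would be 3.4 to 10.3 points.

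**5. Effect on confirmation.** Protocol 8.1 and SAP 14.1.1 require a second qualifying assessment at least 4 weeks after the first. A participant with PR at Day 57 who stops for toxicity before a confirming scan gets none under literal 4.1. Day 57 is 8 weeks after start, past the 6-week minimum for SD, so her confirmed best response would be SD and she would count as a non-responder. One responder can decide the criterion in step 1.

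**The case against.** A reader might infer that 7.1 and the follow-up text leave only safety and survival contacts, and that a responder who stops for toxicity loses DOR, DRR and PFS altogether. The documents do not support either. Section 7.1 refers onward to the Schedule of Activities, which contains note j. Long-term Follow-up covers progression as well as survival and is tied to the same schedule. Section 8 makes adherence to that schedule mandatory. DOR and PFS are censored, so the participant still contributes her follow-up to the Kaplan-Meier estimate; in the example she contributes 1.87 months of DOR.

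The DRR effect is also conditional:
- It arises under Protocol Table 11 only if censoring falls before 6 months.
- SAP 14.6 counts every censored DOR as not durable, so the example responder, still controlled at Day 281, would fail there even with note j scans. That is a separate Protocol/SAP conflict.
- The primary analysis falls 8 months after last accrual, 8 × 30.4375 = 243.5 days. The last participants cannot have a Day 281 scan by then under either rule.
- Participants who start new anticancer therapy are censored in any case.

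The clause may simply be carried-over text: it closely matches the treatment-stop wording in SAP 13. That is an inference, but a plausible one. Finally, SAP 4.1 states that after early discontinuation no efficacy analyses will be performed.

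All of this stands, and it narrows the point. It does not remove the contradiction between 4.1 and note j. It also does not put the ORR out of reach, because confirmation can fail for want of a scan.

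**Conclusion.** The contradiction is real, and 4.1 is the outlier. The silence on imaging in the 7.1 follow-up bullet and the remote default for Long-term Follow-up add ambiguity but are not separate stop rules.

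If 4.1 were followed literally, DOR and PFS would be truncated at the last on-treatment scan, possibly informatively. DRR would fall by 3.4 points for each otherwise durable responder censored before 6 months, under the Protocol Table 11 rule and nominal scan days. A first response could go unconfirmed.

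The total effect cannot be computed, because the documents give no rate of toxicity stops among responders and no indication of which text sites followed. N = 29 and the 81% are unchanged. For this study's reported efficacy the effect is nil, since those analyses are cancelled. The wording still matters as a rule in the protocol, whose section 4.2 foresees that further cohorts might be added.

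**What to change.** Three wording changes, all in the Protocol:

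- **4.1:** delete unacceptable toxicity from the tumor-evaluation sentence and use note j's two ends, confirmed PD or study discontinuation. Keep the word confirmed, since 7.1 distinguishes initial from confirmed PD and dropping it would create a new conflict with note j.
- **7.1:** in the list of what follows discontinuation, add a pointer to tumor evaluation per Table 1 note j for participants who stop for a reason other than PD.
- **1.1 and 4.1:** state that telephone or chart follow-up does not replace scans scheduled by note j.

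The cost is text only. Note j and 8.1 already schedule the imaging, and no treatment-stopping rule, sample size or power figure changes. The different handling of censored DOR in Protocol Table 11 and SAP 14.6 needs its own reconciliation.
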